### **7.8.2      Laboratory data**

Laboratory data will be presented as per the time point or visits specified in CTP. Listing of laboratory test status (Performed/ Not performed/ Unknown/ Performed but missing value) at visit 1 and (Performed/ Not performed/ Unknown) for further visits will be presented by therapy prescribed. Listings of laboratory results, units, lower and upper limits, range (Normal/Out of range/Unknown), if out of range then Clinical Significance status (Clinically Significant/Non Clinically Significant) for lab tests like clinical biochemistry, liver function test (LFT), urinalysis, coagulation test, immunological test and arterial blood gas etc. will be presented by therapy prescribed for each patient for each suggested visits. In addition to this after visit 1, if the out of range lab test results are clinically significant then Relationship with Nintedanib (Related to Nintedanib/ Not Related to Nintedanib) will also be presented. Values outside of the laboratory's reference limits (i.e., those with high or low values) will be flagged in the laboratory listings.

Laboratory tests with continuous results and their changes from baseline for each suggested visits will be summarized descriptively by therapy assigned. For categorical data will be summarized using frequency and proportion.

Frequency count with percentage for possibly clinically significance abnormalities will be presented separately by visits.

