 - GERD medication
 - PDE-5 inhibitor
 - Endothelin receptor antagonist
 - Long-term Oxygen therapy

- Listed for lung transplantation
- NSAIDs
- Hormonal contraceptives
- Hormone replacement therapy
- Anti-VEGF drugs
- Chemotherapy
- Other, please specify

Laboratory tests at visit 1 (performed/not performed/unknown/performer but missing value and value (units), date):

- Liver function test (ALT, AST, GGT, ALP, Total Bilirubin)
- Other biochemical test (Cr, CK, BNP, CRP, LDH)
- Coagulation test (PT-INR, APTT)
- Immunological test (ANA, RF at visit 1 only)
- Urinalysis (Occult blood in urine by dipstick)
- Arterial blood gas (PaO₂, PaCO₃)

After visit 1, abnormal lab values that are clinically significant and related to Nintedanib will be collected as Adverse Event in eCRF and will be reported on NIS AE form.

[After visit 1, lab results will be collected in eCRF in following manner:

- Laboratory tests – done/not done/unknown
- If done – within normal range/unknown/out of range
- If out of range - clinically significant/clinically not significant
- If clinically significant – related to the Nintedanib/not related to Nintedanib
- If related to the Nintedanib – it will be reported on the AE page (In addition to the AE term, actual lab values that are abnormal, clinically significant & related to Nintedanib will also be reported in the CRF)]

In addition to this, any abnormal lab value, which is clinically significant and qualifies as SAE, will be reported in the eCRF and NIS AE form whether or not it is related to the Nintedanib.

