10.4 DATA SOURCES

This active surveillance is based on existing and newly collected data at selected centers where IPF patients are regularly treated.

Data of the individual patients will be gathered using electronic data capture (EDC) system. The medical records of Group A and B patients will be used to collect the data of covariates as described in [section 10.3.3](#) and all ADRs and SAEs occurring during the duration of the treatment/ 52 weeks, whichever is earlier. This data will be entered into eCRF and reported via NIS AE form as per [section 12.2](#). Group B and C patients will be followed-up according to clinical practice for at least 52 weeks/discontinuation (whichever is earlier) from the start of the treatment, at regular intervals (i.e. approximately every 4 weeks for the first 3 visits and every 12 weeks thereafter till week 52). After the completion of medical examination and observation at the suggested time points, investigator needs to enter data of the registered patients (all ADRs and SAEs) in the EDC system and report via NIS AE form as per [section 12.2](#). Additionally information on certain covariates will be collected at subsequent visits as described in the [section 10.3.3](#). For patients treated with Pirfenidone, only baseline characteristics will be recorded in EDC and these patients will not be followed.

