10.7.1 Analyses of outcome events

All outcome events are based on reported AE data which will be handled according to BI standards (see the section below). In addition, patients for all analysis will be stratified by (i) no prior IPF treatment (ii) prior Pirfenidone treatment (switch) (iii) other prior treatment used for the management of IPF (switch) (iv) other prior treatment used for the management of IPF (add-on). In case of conflicting results the results of the first strata [(i) no prior IPF treatment] are decisive, because in new users potential bias is the smallest.

Safety:

In general, safety analyses will be descriptive in nature, and will be based on BI standards, and will focus on all ADRs and SAEs.

AEs will be coded using the current version of the Medical Dictionary for Regulatory Activities (MedDRA) and will be based on the concept of treatment emergent AEs. To this end, all AEs occurring between first intake of Nintedanib prescribed at visit 1 and up to 52 weeks/discontinuation will be considered 'treatment emergent'. An AE is considered to be an ADR if either the physician who has reported the AE or the sponsor assesses its causal relationship as 'related'.

The frequency and incidence of ADRs and SAEs will be tabulated by system organ class and preferred term.

No imputation is planned for missing AE data except for missing onset dates which will be handled according to BI standard.

Descriptive statistics will be calculated for laboratory tests, vital signs and physical examination.

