### **3 INTRODUCTION**

"As per ICH E9, the purpose of this document is to provide a more technical and detailed elaboration of the principal features of the analysis described in the protocol and to include detailed procedures for executing the statistical analysis of the primary and secondary variables and other data.

This TSAP assumes familiarity with the Clinical Trial Protocol (CTP) version 5.0, dated [REDACTED] and Case Report Form (CRF) version final 3.0, dated [REDACTED]. In particular, the TSAP is based on the planned analysis specification as written in CTP Section 10.7 'Data Analysis'. Also the 6 subjects (Subject ID: [REDACTED], [REDACTED]) enrolled in the study based on inclusion\exclusion criteria of protocol version 2.0, dated [REDACTED] and remaining subjects are on protocol version 5.0. Therefore, TSAP readers may consult the CTP for more background information on the study, e.g., on study objectives, study design and population, treatments, definition of measurements and variables, planning of sample size." This TSAP is to contain the analysis specification for a status report of the active surveillance to be submitted to DCGI annually and for the final analysis SAS® version 9.4 will be used for all analyses.

This is an active surveillance study and aim of this study to monitor the real world safety in Indian patients prescribed nintedanib for the treatment of Idiopathic Pulmonary Fibrosis (IPF). The scientific objective of this active surveillance is to obtain an estimate of the occurrence of all ADRs and SAEs in IPF patients prescribed nintedanib per the approved label in the real world setting. In addition, this study will also calculate the percentage of patients who require dose reductions, interruptions and discontinuation due to adverse events. This would help in assessing the safety of nintedanib in IPF patients in Indian real world setting.

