## **6.6 HANDLING OF MISSING DATA AND OUTLIERS**

No missing data analysis is planned for this study. Missing values will be considered as missing, no imputation will be done for the analysis purpose.

No imputation is planned for missing AE data except for missing or incomplete AE onset dates which will be imputed according to BI standards  (i.e. “Handling of missing and incomplete AE dates”) as below.

Step 1: For each missing / incomplete AE onset date, an interval (INT\_START, INT\_END) is defined. The true unknown analysis start date of AE is assumed to be within the interval.

Scenario of AE onset date	INT_START	INT_END
Completely missing AE onset date	Min (AE end date, Date of informed consent)	Min (AE end date, Date of last visit)

Scenario of AE onset date	INT_START	INT_END
Only year of AE onset date is non-missing	Min (AE end date, 01 JAN of the reported year)	Min (AE end date, 31 DEC of the reported year)
Only year and month of AE onset date is non-missing	Min (AE end date, 01 of the reported month)	Min (AE end date, Last date of the reported month)

Note: Completely missing AE end date will not be considered in this derivation step.

Partially missing AE end date will be temporarily assigned the largest possible date in the observed year or month in the derivation step.

Step 2: Derive an imputed AE onset date based on the interval from step 1.

Scenarios	TESS/ Non-TESS	Imputed AE onset date
1. Date of first drug administration is within the interval [INT_START, INT_END]	TESS	Date of first drug administration
2. Date of first drug administration is before INT_START*	TESS	INT_START from step 1
3. Date of first drug administration is after INT_END or missing	Non-TESS	INT_END from step 1

TESS- Treatment emergent AE

\*Note: If INT\_START is after the date of the last drug administration plus residual effect period, then the AE is non-TESS.

Step 3: The AE onset date imputation flag(s) are set according to the level of imputation performed and the standard CDISC rules for imputation or the legacy data imputation rules.

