## **7 PLANNED ANALYSIS**

- All study data will be included in individual patient study data listings. In general, all data will be listed by therapy prescribed and by visit (if applicable). The basic data like demographic and baseline characteristics, patient disposition and patient analysis set will be listed and also summarized by therapy prescribed, by Group. All summary tables will represent descriptive statistics for the parameters being analyzed, wherever applicable.
- Numeric presentations:
  - Non-integer numerical data should be presented with decimal point.
  - If the non-formatted data (e.g. which is received from the clinical database) is inconsistently presented, a decision on how to present the final data will be made on a case-by-case basis.
  - When rounding is required, number 4 or below will be rounded down and number 5 or above will be rounded up.
  - When deriving new variable(s) based on raw data, no rounding will be performed at intermediate calculation. Rounding will only be performed when displaying data.
  - Descriptive analysis for continuous data will include number of non-missing observations (n), mean, standard deviation (SD), median, minimum, maximum, Q1, and Q3. Means, medians, Q1 and Q3 will be rounded to 1 decimal place more than the original data. Standard deviation will be rounded to 2 decimals place more than the original data. Minimum and maximum will be displayed with the same decimal precision as the original data.
  - For categorical data, frequency and percentage with corresponding 95% confidence interval will be presented wherever applicable. Confidence interval and percentages will be rounded to 1 decimal place. Percentages equal to 100 will be output as '100'. The counts and percentages equal to 0 will be represented as '0' only.
- Missing data will not be imputed but will be analyzed as missing.

- Baseline assessments are the assessments taken at the Visit 1 for all patients. If there are multiple assessments collected on the same scheduled time, the average of these assessments will be used.
- The change from baseline is defined as the post-baseline value minus the baseline value.
- Text column should be left justified.
- All the data analysis will be done using SAS® version 9.4.

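### SAP 7.8.2 plans laboratory means and change from baseline at every visit, but protocol 10.3.3 seeks numeric results routinely only at visit 1 and later records values only for selected abnormal results

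*SAP*

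**What the plan says.** **Analysis.** SAP 7.8.2 (Laboratory data) plans: "Laboratory tests with continuous results and their changes from baseline for each suggested visits will be summarized descriptively by therapy assigned". SAP 7 defines change as the post-baseline value minus the baseline value, with baseline at visit 1. Protocol 10.7.1 has a more general statement with no visit limit: "Descriptive statistics will be calculated for laboratory tests, vital signs and physical examination".

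**Collection.** Protocol 10.3.3 asks for a value, units and date at visit 1. After visit 1 the eCRF takes a chain of categories: test done or not, in or out of range, clinically significant or not, related to nintedanib or not. Numbers enter by two routes only:

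- Results at the end of that chain: "actual lab values that are abnormal, clinically significant & related to Nintedanib will also be reported in the CRF".
- Results that are serious, whether or not related: "any abnormal lab value, which is clinically significant and qualifies as SAE, will be reported in the eCRF and NIS AE form".

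**Missing data.** SAP 6.6: "Missing values will be considered as missing, no imputation will be done for the analysis purpose". SAP 7 repeats the rule: "Missing data will not be imputed but will be analyzed as missing".

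**The concern.** A change from baseline needs a number at both ends. Under protocol 10.3.3 most tested patients have one only at visit 1. A later result that is normal, or abnormal but not clinically significant, or judged unrelated and not serious, leaves no number behind. Whether a value is recorded therefore depends on the value itself, so the gaps are not missing at random. With no imputation, the visit-wise mean is taken over the patients who qualified by being abnormal.

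The liver tests matter most. Protocol section 8 says nintedanib is associated with rises in liver enzymes and bilirubin. A mean restricted to clinically significant abnormal results would overstate the average rise in the cohort. The n beside the mean would show that few patients contribute, but not that they were selected on the outcome. If the selected values are held only on the AE page, the tables would be empty and the planned analysis could not be delivered.

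The layout by therapy adds a smaller gap. Pirfenidone patients are not followed (protocol 10.1), so that column can hold no change from baseline at all.

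**Working it through.** The documents give no figure on this point, so there is nothing to reproduce. The check compares the texts, counts the affected summaries, and illustrates the consequence.

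**1. What is needed against what is collected**

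| Item | Needed for SAP 7.8.2 | Collected under protocol 10.3.3 |
|---|---|---|
| Visit 1 | Numeric value | Value, units and date (or: not performed, unknown, value missing) |
| Later visit, result in range | Numeric value | Category only |
| Later visit, out of range, not clinically significant | Numeric value | Category only |
| Later visit, clinically significant, unrelated, not an SAE | Numeric value | Category only |
| Later visit, clinically significant and related | Numeric value | Value recorded |
| Later visit, clinically significant and SAE-qualifying | Numeric value | Reported, related or not |

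Two other places support this reading. The registration list in protocol 10.2.2.3 names laboratory tests at visit 1, while it names pulmonary function tests and co-medications at visit 1 and later visits. SAP 7.8.2 itself has a status code for a test performed with its value missing at visit 1, but not at further visits, as one would expect if there is no value field later.

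**2. Summaries affected**

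Tests with continuous results in protocol 10.3.3:

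- liver: ALT, AST, GGT, ALP, total bilirubin = 5
- other biochemistry: Cr, CK, BNP, CRP, LDH = 5
- coagulation: PT-INR, APTT = 2
- arterial blood gas: 2 values
- total: 5 + 5 + 2 + 2 = 14

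ANA and RF are left out because they are marked as visit 1 only, and urinalysis because it is a dipstick result.

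Follow-up visits, from protocol 10.4 ("approximately every 4 weeks for the first 3 visits and every 12 weeks thereafter till week 52"): about weeks 4, 8 and 12, then about weeks 24, 36 and 48–52, so 3 + 3 = 6.

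- All tests: 14 × 6 = 84 test-by-visit summaries.
- Liver tests: 5 × 6 = 30.

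**3. Illustration of the bias**

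The documents do not give the share of tests with a recorded value. The assumptions here are mine: values are normal with the same mean and SD at both visits, there is no true change, only the highest fraction q of follow-up values is recorded, and the correlation between baseline and follow-up is ρ. The mean recorded change in SD units is then

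(1 − ρ) × φ(z₁₋q) / q

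The expected number of values per visit is 200 × q, if all 200 nintedanib patients are tested.

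| q | Patients with a value | ρ = 0.3 | ρ = 0.5 | ρ = 0.7 |
|---|---|---|---|---|
| 2% | 4 | 1.69 | 1.21 | 0.73 |
| 5% | 10 | 1.44 | 1.03 | 0.62 |
| 10% | 20 | 1.23 | 0.88 | 0.53 |

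Over this range, a drug with no effect on the test would show a mean rise of about 0.5 to 1.7 SD. This shows the direction and that the effect need not be small. It is not an estimate for this study.

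**The case against.** The strongest objection is that the deciding document is not available. The SAP was written against "Case Report Form (CRF) version final 3.0", which is not supplied, and the protocol's flow chart is not in the supplied text either. SAP 7.8.2 plans listings of results, units and limits for each patient at each suggested visit, and the SAP history table says the section was updated for laboratory information collected after visit 1. The eCRF may therefore hold numeric fields at later visits. In protocol 10.3.3 only the immunological tests carry an explicit visit-1-only tag, which would be redundant if it applied to every test. **This stands as a reason for caution.** It decides which document is wrong, not whether the two agree: if the eCRF captures every result, protocol 10.3.3 misdescribes collection.

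SAP 7.8.2 also opens by tying laboratory presentation to the visits given in the protocol. That does not resolve the conflict, because the same section goes on to require change from baseline at each suggested visit.

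Three further points are fair:

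- At visit 1 values are sought from all patients but may be missing.
- SAP 7.8.2 already plans categorical summaries and a by-visit count of clinically significant abnormalities, so part of the remedy exists.
- The count of 84 is a number of table entries, not an effect size.

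The practical harm is also bounded. The tables are descriptive, and related, clinically significant abnormalities still reach the primary outcome as ADRs through the AE page. That limits the importance of the point but does not make the planned means valid.

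**Conclusion.** The concern holds. Followed as written, protocol 10.3.3 and SAP 7.8.2 cannot both be carried out with a valid result: none of the roughly 84 change-from-baseline summaries, including about 30 for liver tests, would hold numeric values from all tested patients. They would be selected on the outcome or empty.

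This assumes that the eCRF collects what protocol 10.3.3 describes. If it records more, the SAP tables can stand and the protocol needs correcting. Confidence is medium for that reason. The change should be made, but it concerns supportive safety output and leaves the primary and secondary outcomes untouched.

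**What to change.** 1. Check whether eCRF final 3.0 has a numeric result field at later visits that is completed whenever a test was done.
2. **If it does not:** in SAP 7.8.2, restrict continuous laboratory summaries to visit 1. For each later visit and test, tabulate patients tested, out of range, clinically significant, and clinically significant and related, with patients tested as the denominator. The by-visit count already planned states no denominator. Put the selectively recorded values in a listing only.
3. **If it does:** keep change from baseline, for nintedanib patients only, and amend protocol 10.3.3 to describe the collection as it is.
4. Align the laboratory statement in protocol 10.7.1 with whichever applies.

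Vital signs and pulmonary function tests are outside this request.

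The cost is one eCRF check and some rewording; where step 2 applies, there are also fewer tables. No new data are needed. Under step 2 the mean-change laboratory table is lost, but the data the protocol describes cannot support it.

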### **7.8.3      Vital signs and Physical Examinations**

Vital signs and Physical examinations assessments will be performed at the time points or visits specified in CTP. Vital sign and physical examination results (including heart rate, systolic and diastolic blood pressure, height, weight and pregnancy status) will be listed by therapy prescribed and by site and patient. Also, continuous results of vital sign and physical examinations and their changes from baseline for each suggested visits will be summarized descriptively (n, mean, SD, median, minimum, and maximum) by therapy prescribed.

### **7.8.4      ECG**

[figure not shown]
This section is not applicable as no ECG data are collected.

### **7.8.5      Others**

Pulmonary function test result will be performed as per suggested visits specified in CTP. Pulmonary function test results will be listed by therapy prescribed and by site and patient. Descriptive statistics for results of pulmonary function test and its change from baseline for each suggested visits will be presented by therapy prescribed.

## **10 HISTORY TABLE**

Table 11: 1 History table

Version	Date	Author	Sections Changed	Brief description of change
Final 2.0	15-Mar-2019	[REDACTED]	3.0 and 6.2	Important Violation table 6.2:1 (CTP version 2.0) removed and Table 6.2:2 renamed as 6.2. Also, Introduction section 3 updated accordingly.
Final 2.0	26-Feb-2019	[REDACTED]	3.0 and 6.2	This section is updated according to CTP version 2.0 and CTP version 5.0 as 6 subjects enrolled in the study based on CTP version 2.0 and remaining on CTP version 5.0.
Final 2.0	10-Jan-2019	[REDACTED]	2.0	Updated list of abbreviations as applicable
			3.0	Updated for protocol and CRF versions and interim analysis is replaced by annual status report submission to DCGI. Replaced suspected ADRs (serious and non-serious), serious and fatal AEs by “all ADRs and SAEs” and added ‘interruptions’ term as per updated protocol text.
			4.0	Protocol version updated
			5.1	Occurrence of ADRs (serious and non-serious) is replaced by Incidence of all ADRs in nintedanib treated patients. Occurrence of AEs (serious and fatal) is replaced by Incidence of all SAEs in nintedanib treated patients as per updated protocol.
			5.2.2	Interruptions term is added.
			[REDACTED]	[REDACTED]
			6.1	Updated for the group wise definitions according to protocol version 5.0.

			6.2	IPV for Enrolled pregnant patients is removed and updated all the IPVs as per version 5.0 of protocol.
Version	Date	Author	Sections Changed	Brief description of change
			6.3	Definitions of Screened and Treated set are updated according to Groups.
			6.6	Note is added for completely and partially missing AE end date.
			6.7	Updated for visit information as per Groups.
			7.0	Removed Significant digit related rules as significant digit concept is not used for this study. The text “Baseline characteristics of consecutive 100 IPF patients not treated with nintedanib will be used to compare the patients profile with the patient treated with nintedanib and will allow to put the safety date of nintedanib into perspective.” has been removed.
			7.1	Added text “At visit 1, the baseline characteristics (e.g. demographics, pulmonary function tests, HRCT evaluation etc.,) will be recorded for all patients (either treated with nintedanib or pirfenidone) from the same centre during the same time period.” Added Table 7.1 The classification of mMRC dyspnea scale.
			7.2	Updated section and removed the text “Previous medication used for IPF prior to baseline/visit 1 assessment and co-medications for IPF at visit 1 and further visits (i.e. during surveillance) will be listed separately.” Added text as “Prior IPF treatments (Pirfenidone or Other) for patients prescribed Nintedanib will be listed separately by site and patients.”
			7.4	Updated primary and secondary outcomes as per version 5.0 protocol. Added text “All analyses of AEs will be based on the number of patients with

Version	Date	Author	Sections Changed	Brief description of change
			7.5.2	Added “interruptions” word.
			7.7	Updated text as “Exposure to nintedanib will be estimated as time from the day nintedanib is initiated until 52 weeks or discontinuation of the drug (or the final contact with the patient for the last regular observation/end of the study).”
			7.8	Updated as per ADRs and SAEs terminology and added “pulmonary function test” in the listed evaluations.
			7.8.1	Updated this section as for AEs as per protocol version 5.0.
			7.8.2	Updated laboratory test related information collected after Visit 1. Also additional information is updated as per CRF at visit 1.
			7.8.3	Modified text from “by patients” to “by site and patients”.
			7.8.5	Modified text from “by patients” to “by site and patients”. Deleted Section 8 for Interim analysis.
			[REDACTED]	[REDACTED]
Final 1.0	24-May-2018	[REDACTED]	None	This is the final version 1.0 of TSAP with necessary information for trial conduct
